4.2.3. Sensitivity analyses

As for the main analytical approach an ANCOVA model will be performed with the treatment group and age category (age at vaccination: 65-69, 70-79 or ≥ 80 years) as fixed effects, **center as random effect** and the pre-dose \log_{10} -transformed titer as covariate.

In case the model with random effect does not converge we proceed with center as a fixed effect.

Here is an example of SAS code that will be used:

```
proc mixed data=data_in;
  class agecat trt_grp center;
  model log10(titer day x) = log10(pre_dose) agecat trt_grp;
  random intercept/subject=center;
  lsmeans trt_grp/cl pdiff alpha=0.05;
run;
```

4.3. Secondary Endpoints Analyses

4.3.1. Immunogenicity analysis

The primary analysis of secondary immunogenicity endpoints will be based on the PPS for analysis of immunogenicity. If, in any vaccine group, the percentage of vaccinated participants with serological results excluded from the PPS for analysis of immunogenicity is 5% or more, a second analysis based on the ES will be performed to complement the PPS analysis.

4.3.1.1. Between groups assessment

- The asymptotic standardized 95% CI for the difference in seroconversion rate (Control group minus Co-Ad group) will be computed at 1 month after the FLU vaccine (i.e., at Day 31 [Visit 2] for both groups).

Reference criteria for evaluation of non-inferiority:

The upper limit of the 2-sided 95% CI on the group difference (Control group minus Co-Ad group) in seroconversion rate is $\leq 10\%$ for anti-HI antibodies.

All between groups analyses of secondary endpoints presented in this section will be descriptive with the aim to characterize the difference in immunogenicity between groups. These descriptive analyses should be interpreted with caution considering that there is no adjustment for multiplicity for these comparisons.

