9.3.2. Secondary endpoints/estimands analyses

- Method for evaluation of non-inferiority of the FLU vaccine in terms of HI seroconversion rate (SCR) for each of the FLU vaccine strains at one month after the FLU vaccine dose (i.e., at Day 31 for both groups):
 - The 2-sided 95% CI on group difference in SCR (Control group minus Co-Ad group) will be computed based on the method of Miettinen and Nurminen [Miettinen, 1985].
 - Reference criteria for evaluation of non-inferiority:
The UL of the 2-sided 95% CI on the group difference (Control group minus Co-Ad group) in SCR is $\leq 10\%$ for anti-HI antibodies.
- The other secondary endpoints are described in Section 3. Descriptive analyses of demography, immunogenicity, and safety will be detailed in the SAP.

Table 20 Definitions of SCR, SPR and MGI

Abbreviation/Term	Definition
HI SCR	The percentage of vaccinees who have either a HI pre-dose titer $< 1:10$ and a post-dose titer $\geq 1:40$ or a pre-dose titer $\geq 1:10$ and at least a 4-fold increase in post-dose titer.
HI SPR	The percentage of vaccinees with a serum HI titer $\geq 1:40$ that usually is accepted as indicating protection.
MGI	The geometric mean of the within-participant ratios of the post-dose titer over the pre-dose titer.

HI = hemagglutination inhibition; SCR = seroconversion rate; SPR = seroprotection rate; MGI = mean geometric increase

- Additionally, the Center for Biologics Evaluation and Research (CBER) and Committee for Medicinal Products for Human Use (CHMP) criteria for HI SPR and SCR will be assessed as follows:

CBER's criteria:

- The lower limit (LL) of the 95% CI for SCR should be $\geq 30\%$ in participants ≥ 65 YOA.
- The LL of the 95% CI for SPR should be $\geq 60\%$ in participants ≥ 65 YOA.

CHMP's criteria:

At least one of the 3 following criteria should be met:

- The point estimates of SPR $> 60\%$, SCR $> 30\%$, and MGI > 2.0 for elderly ≥ 60 YOA for each of the antigen strains.

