The nominal power to evaluate the non-inferiority on SCR for each of the FLU strains is above 86%, depending on the plausible rates.

Table 22 Evaluation of non-inferiority in terms of HI antibody SCR when FLU aQIV is co-administered with the RSVPreF3 OA investigational vaccine compared to FLU aQIV when administered alone assuming approximately 462 participants are available in each group for a range of plausible SCRs (Amended: 13 December 2022)

N evaluable participants per group	Threshold	Plausible rates in Control group**	Type II error	Nominal Power
FLU vaccine: Non-inferiority* in terms of SCR				
462	10%	70%	8.7%	91.3%
462	10%	50%	13.9%	86.1%
462	10%	35%	11.0%	89.0%
462	10%	25%	6.1%	93.9%

SCR = Seroconversion Rate.

*Pass 2019 alpha = 2.5%, for SCR – Non-inferiority: Proportions – Two independent Proportions – Non-Inferiority Tests for the Difference Between Two Proportions.

** SCR observed in the Control group in Zoster-004 study range from 35.3% to 60.9%.

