4. STATISTICAL ANALYSES

4.1. General Considerations

4.1.1. General Methodology

95% CI for proportion will be based on exact Clopper-Pearson CI [[Clopper](#), 1934].

95% CI for group difference in proportion will be based on Miettinen and Nurminen CI [[Miettinen](#), 1985].

The group adjusted GMT ratio will be based on a back transformation of group contrast in an ANCOVA model applied to the logarithm-transformed titers.

Primary Analysis: The ANCOVA model will include the treatment group and age category (age at vaccination: 65-69, 70-79 or ≥ 80 years) as fixed effects and the pre-dose log-10 titer as regressors.

Sensitivity Analysis: The ANCOVA model will include the treatment group and age category (age at vaccination: 65-69, 70-79 or ≥ 80 years) as fixed effects, center as the random effect and the pre-dose log-10 titer as regressors.

95% CI for GMT and GMT ratio will be based on a back transformation of student CI for the mean and difference of means (for GMT ratio) respectively of log-transformation (i.e., $10^{\wedge}CI$).

4.1.2. Definition:

- For all endpoints:

The baseline value will be the latest pre-dose assessment with a non-missing value, including those from unscheduled visits. If time is not collected, Day 1 assessments are assumed to be taken prior to first dose and used as baseline.

MG1 (mean geometric increase): The geometric mean of the within participant ratios of the post-dose titer over the pre-dose titer.

- For the RSV antigens:

A seronegative participant will be defined as a participant whose antibody titer/concentration is below the cut-off value of the assay. A seropositive participant is a participant whose antibody titer/concentration is greater than or equal to the cut-off value of the assay.

- For the FLU antigens:

SCR (seroconversion rate): The percentage of vaccinees who have either a HI pre-dose titer $< 1:10$ and a post-dose titer $\geq 1:40$ or a pre-dose titer $\geq 1:10$ and at least a four-fold increase in post-dose titer.

HI SPR (seroprotection rate): The percentage of vaccinees with a serum HI titer $\geq 1:40$ that usually is accepted as indicating protection.

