5. SAMPLE SIZE DETERMINATION

The **target enrollment** will be **1028 participants** (514 in the group receiving the RSVPreF3 OA investigational vaccine co-administered with FLU aQIV [Co-Ad group] and 514 in the Control group where RSVPreF3 OA investigational vaccine and FLU aQIV are administered in a sequential manner). This allows to obtain at least 924 **evaluable participants** (462 in the Co-Ad group and 462 in the Control group) for the

evaluation of the primary objectives, assuming that 10% of the enrolled participants will not be evaluable.

Participants who withdraw from the study will not be replaced.

Each objective will be evaluated with a nominal type I error of 2.5%.

Table 3 Overall power to demonstrate primary objectives: non-inferiority of the immunogenicity of the RSVPreF3 OA investigational vaccine when co-administered with FLU aQIV compared to when administered alone – assuming approximately 462 participants are available in each group

Endpoint	Standard deviation of \log_{10} concentration	Reference ratio	Non inferiority margin	Type II error	Power
FLU non-inferiority* (1-sided test with alpha=2.5%)					
GMTs HI H1N1 strain	0.6	1.05	1.5	2.5%	97.5%
GMTs HI H3N2 strain	0.6	1.05	1.5	2.5%	97.5%
GMTs HI B/Yamagata	0.6	1.05	1.5	2.5%	97.5%
GMTs HI B/Victoria strain	0.6	1.05	1.5	2.5%	97.5%
RSV non-inferiority* (1-sided test with alpha = 2.5%)					
GMTs RSV-A neutralization antibody	0.45	1.05	1.5	0.1%	99.9%
RSV non-inferiority* (1-sided test with alpha = 2.5%)					
GMTs RSV-B neutralization antibody	0.45	1.05	1.5	0.1%	99.9%
Global Type II error to show non-inferiority				~10.0%	
Global power					~90.0%

GMT = geometric mean titer; **HI** = hemagglutination inhibition; **RSV** = respiratory syncytial virus

*Pass 2019 alpha = 2.5%, Two-Sample T-Tests for Non-Inferiority Assuming Equal Variance and Equal mean

For RSV: non-inferiority limit = 0.176 (=log10[1.5]).

For each FLU vaccine strain: non-inferiority limit = 0.176 (=log10[1.5]).

Reference Ratio= 0.0212 (=log10[1.05])

Considering a potential slight interference of 1.05 in true GMTs in both groups with a common population standard error of 0.45 for the RSV-A and RSV-B neutralization antibodies and 0.6 for each of the FLU strains in \log_{10} transformed concentration, the study has at least 90.0% power to meet the primary objectives.

Nominal powers to evaluate the secondary objective

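### The secondary seroconversion-rate comparison could gain a little precision at almost no cost by adjusting for pre-dose HI titer and age category, as the GMT comparisons already do

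*SAP*

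**What the plan says.** The SCR difference is Control minus Co-Ad at Day 31, one comparison per influenza strain. SAP 4.3.1.1 states "The asymptotic standardized 95% CI for the difference in seroconversion rate (Control group minus Co-Ad group) will be computed", and non-inferiority is judged by whether the upper limit of the difference "in seroconversion rate is $\leq 10\%$ for anti-HI antibodies". SAP 4.1.1 gives the general method: "95% CI for group difference in proportion will be based on Miettinen and Nurminen CI". Protocol 9.3.2 agrees that the interval "will be computed based on the method of Miettinen and Nurminen". None of these places names a stratum or covariate, and no adjusted SCR analysis is listed as a sensitivity analysis. Age enters SCR only through the within-group tables of SAP 4.3.1.2.

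The GMT ratios for the same strains and day come from an ANCOVA that includes age category and the log10 pre-dose titer (Protocol 9.3.1, SAP 4.2.2). Protocol 6.3.3 makes age category and center the minimization factors. Seroconversion is defined from the pre-dose titer: below 1:10 it requires a post-dose titer of at least 1:40, otherwise a four-fold rise.

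SAP 4.3.1.1 labels the between-group secondary analyses as descriptive, without multiplicity adjustment. On power, Protocol 9.5 says "The nominal power to evaluate the non-inferiority on SCR for each of the FLU strains is above 86" percent.

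**The concern.** The same trial compares the same strains on the same day in two ways, adjusting one for two baseline variables and not the other, and gives no reason. The hurdle for seroconversion changes with the pre-dose titer, so a participant's chance of clearing it generally depends on that titer. Where a baseline variable predicts the outcome, conditioning on it gives a narrower interval and corrects for chance imbalance.

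SCR is also where the plan has least room. Its stated power is 86.1% to 93.9% per strain, against 97.5% per strain for the HI GMTs and 99.9% for RSV-A and RSV-B. What is at stake is some avoidable width in a secondary comparison. A chance difference in pre-dose titers would also move the SCR difference, while the adjusted GMT ratio would allow for it.

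**Working it through.** **Inputs from the documents.** n = 462 evaluable per group ("462 in the Co-Ad group and 462 in the Control group", SAP 5); margin 0.10; one-sided alpha 2.5%, i.e. the upper limit of a two-sided 95% CI; control SCRs of 70, 50, 35 and 25% (Protocol Table 22, SAP Table 4). The enrollment figure is consistent: "assuming that 10% of the enrolled participants will not be evaluable", and 462/0.9 = 513.3, rounded up to 514.

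**Step 1: reproduce the stated power.** With a true difference of 0 and equal rates p, SE = √(2p(1−p)/n) and power = Φ(0.10/SE − 1.96).

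- p = 0.50: SE = √(0.5/462) = 0.03290; power = Φ(3.040 − 1.96) = 86.0% (stated 86.1%)
- p = 0.70: SE = 0.03015; power 91.3% (stated 91.3%)
- p = 0.35: SE = 0.03138; power 89.0% (stated 89.0%)
- p = 0.25: SE = 0.02849; power 93.9% (stated 93.9%)

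A restricted-variance score version gives 86.2% at p = 0.50. The stated figures are sound for the crude comparison.

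**Step 2: effect of adjustment.** If pre-dose titer and age explain a share R² of the SCR variance, the variance of the difference is multiplied by (1 − R²). The documents give no R², so 0.02 to 0.10 is assumed. At p = 0.50:

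| R² | SE | CI half-width (points) | Power |
|---|---|---|---|
| 0 | 0.03290 | 6.45 | 86.0% |
| 0.02 | 0.03257 | 6.38 | 86.7% |
| 0.05 | 0.03206 | 6.28 | 87.7% |
| 0.10 | 0.03121 | 6.12 | 89.3% |

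**Step 3: is that range plausible?** Two simulations apply the plan's seroconversion definition with post-dose log10 SD 0.6; the other inputs are assumed.

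- Pre-dose mean 1:20, pre-dose SD 0.4 or 0.6, pre/post correlation 0.4 or 0.7, SCR 50%: pre-dose titer in three categories (<1:10, 1:10 to <1:40, ≥1:40) explains about 1.4-7% of SCR variance (power about 86.5-88.3%). Flexible adjustment explains about 3-10% (about 87.0-89.3%).
- Pre-dose SD 0.5, pre/post slope 0.3 to 0.9, a modest age effect, SCR 35% or 50%, 1,500 trials per scenario, logistic standardization: variance falls by about 2-12% and power rises by about 1-4 points.

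In some scenarios seroconversion was not monotone in pre-dose titer, for example 0.45, 0.60 and 0.42 across the three categories. A single linear log-titer term would miss that pattern.

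**Step 4: chance imbalance.** If the groups differ in mean pre-dose log10 titer by 1.96 standard errors, and the association is roughly linear, the crude SCR difference shifts by √(R²·p(1−p)) × 1.96 × √(2/n). At p = 0.50, 1.96 × √(2/462) = 0.1290.

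- R² = 0.02: 0.0707 × 0.1290 = 0.9 points
- R² = 0.05: 0.1118 × 0.1290 = 1.4 points
- R² = 0.10: 0.1581 × 0.1290 = 2.0 points

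These shifts compare with a 10-point criterion.

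**The case against.** The case for leaving the plan alone is substantial. The unadjusted interval is valid under randomization. Protocol 9.1 ties the statistical hypotheses to the primary objectives, so no confirmatory claim rests on SCR. Age imbalance is largely prevented by minimization. An imbalance in pre-dose titer would be visible, because Day 1 HI GMTs and seroprotection rates are reported by group. The gain is small and rests on an association that the documents do not quantify. All of this stands, and it limits the weight of the point. What remains is that seeing an imbalance does not provide a prespecified way to allow for it, and an adjustment chosen after a near miss would not be credible.

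Three stronger readings are tempting but not supported:

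- A reader might infer that the pre-dose titer is ignored. It is not: it enters each participant's seroconversion status. It is only not conditioned on in the group comparison.
- A reader might infer that the gap between 97.5% and 86.1% shows what adjustment buys. It does not. The GMT power was itself computed with unadjusted two-sample t-tests, at a true ratio of 1.05. The SCR power reproduces at a true difference of 0, and 86.1% is the lowest of four scenarios.
- A reader might infer that the SCR and GMT results would conflict through baseline imbalance alone. Shifts of about 0.9-2.0 points against a 10-point criterion make that possible only near the boundary. The two measures may differ anyway, and no rule requires them to agree.

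A stratified Miettinen-Nurminen interval would stay closer to the protocol's method, but crossing three age with three titer categories gives nine strata. With about 10% of participants targeted at 80 years or older, that is roughly 46 per group in three cells of about 15, and a collapsing rule would be needed.

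**Conclusion.** This is a cheap improvement to a secondary, descriptive comparison, not an error. At an SCR of 50%, true difference 0 and 462 per group, if the covariates explain 2-10% of SCR variance, power rises by about 0.7 to 3.3 points and the half-width falls by about 0.07 to 0.33 points. With only three titer categories the gain could be slightly below that range. Correcting for chance imbalance in pre-dose titer is a benefit of similar modest size. The direction of the gain is well founded; its size depends on pre-dose distributions and pre/post correlations that the documents do not report.

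**What to change.** Prespecify one adjusted analysis per strain: the marginal risk difference (Control minus Co-Ad) obtained by standardization from a logistic model with treatment, age category (65-69, 70-79, ≥80, as in the GMT model) and pre-dose HI titer in categories (<1:10, 1:10 to <1:40, ≥1:40) or another non-linear term. Enter the covariates as main effects, so that no nine-cell stratification or collapsing rule is needed. State how the standard error is computed. Apply the 10% reference criterion to the resulting 95% CI and keep the crude Miettinen-Nurminen interval as supportive. Standardization targets a marginal difference in proportions, as the crude comparison does, so the 10% criterion keeps its meaning.

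Align Protocol 9.3.2 with SAP 4.1.1 and 4.3.1.1. Also revise SAP 4.8, which now declares no departure from the protocol's analyses.

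The cost is wording in both documents and a few lines of code. No new data are needed, and no one in an SCR denominator is lost, because seroconversion as defined already uses the pre-dose titer. One small downside is that the adjusted difference will not exactly equal the difference between the tabulated group rates, so a table footnote should say so.

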4.3.1.2. Within groups assessment

For each group, at each time point that blood samples are collected (except Day 45) for humoral immune response and for each assay (unless otherwise specified):

- Percentage of participants above pre-defined assay cut-off and their exact 95% CI will be tabulated.
- Percentage of participants above seroprotection/seroconversion rate for HI antibody titer and their exact 95% CI will be tabulated.

- GMCs/GMTs and their 95% CI over time will be tabulated and presented graphically (in log10 scale).
- MGI will be tabulated with 95% CI.
- Antibody titer/concentration will be displayed using reverse cumulative curves (both groups and available timepoints (except Day 45) will be presented in the same graph).

The above mentioned descriptive within group immunogenicity analysis will also be generated by age at first vaccination (65-69 YOA, 70-79 YOA, \geq 70 YOA and \geq 80 YOA years).

- Additionally, the CBER and CHMP criteria for HI SPR and SCR will be assessed as follows:

CBER criteria to be evaluated:

- The lower limit (LL) of the 95% CI for SCR should be \geq 30% in participants \geq 65 YOA.
- The LL of the 95% CI for SPR should be \geq 60% in participants \geq 65 YOA.

CHMP criteria to be evaluated:

- At least one of the 3 following criteria should be met:
- the point estimates of SPR $>$ 60%, SCR $>$ 30%, and MGI $>$ 2.0 for elderly $>$ 60 YOA for each of the antigen strains.

These above defined analyses evaluating the CBER and CHMP criteria should be interpreted with caution considering that there is no adjustment for multiplicity for these comparisons.

4.3.2. Safety analysis

The safety analysis will be performed on the ES as follows:

- The number and percentage of participants and doses with at least one administration site event AE (solicited and unsolicited), with at least one systemic AE (solicited and unsolicited) and with any AE during the 7-day (i.e., the day of vaccination and 6 subsequent days) and 30-day (i.e., the day of vaccination and 29 subsequent days) follow-up period will be tabulated with exact 95% CI after each dose and overall. The same computations will be done for Grade 3 AEs, for Grade 3 non-serious AEs and for AEs resulting in a medically attended visit.

These analyses will present all solicited and unsolicited AEs, including SAEs and pIMDs (unless otherwise specified).

The above analysis will also be performed for the solicited symptoms only during the 7-day (i.e., the day of vaccination and 6 subsequent days) follow-up period.

- The number and percentage of participants reporting each individual solicited administration site AE (any grade, Grade 3 and resulting in medically attended visit) and solicited systemic AE (any grade, Grade 3 and resulting in medically attended

visit) during the 7-day follow-up period (i.e., the day of vaccination and 6 subsequent days) will be tabulated for each group after each dose and overall. The percentage of doses followed by each individual solicited administration site AE (any grade, Grade 3 and resulting in medically attended visit) and solicited systemic AE (any grade, Grade 3 and resulting in medically attended visit) during the 7-day follow-up period (i.e., the day of vaccination and 6 subsequent days) will be tabulated, with exact 95% CI.

- For fever, the number and percentage of participants reporting fever by half degree (°C) cumulative increments during the 7-day follow-up period (i.e., the day of vaccination and 6 subsequent days) will be tabulated for each group after each dose and overall.
- The percentage of participants with each solicited administration site event and solicited systemic event (any grade and Grade 3) will be represented graphically for each group after each dose.
- The number of days with solicited events reported during the 7-day follow-up period (i.e., the day of vaccination and 6 subsequent days) will be tabulated for each individual solicited event using descriptive statistics (mean, minimum, Q1, median, Q3, maximum). The same computations will be done for Grade 3 solicited events.
- The number of days with solicited events ongoing beyond the 7-day follow-up period (i.e., the day of vaccination and 6 subsequent days) will be tabulated for each individual solicited event using descriptive statistics (mean, minimum, Q1, median, Q3, maximum). The same computations will be done for Grade 3 solicited events.

All Analyses described above for solicited AEs will be also generated during only the 4-day follow-up period (i.e., the day of vaccination and 3 subsequent days).

- The number and percentage of participants with any unsolicited AEs during the 30-day follow-up period (i.e., the day of vaccination and 29 subsequent days) with its exact 95% CI will be tabulated by group and by Medical Dictionary for Regulatory Activities (MedDRA) System Organ Class (SOC), High Level Term (HLT) and Preferred Term (PT). Similar tabulation will be done for Grade 3 unsolicited AEs, for any causally related unsolicited AEs, for Grade 3 causally related unsolicited AEs and for unsolicited AEs resulting in a medically attended visit. The verbatim reports of unsolicited AEs will be reviewed by a physician and the signs and symptoms will be coded according to the MedDRA Dictionary for Adverse Reaction Terminology. Every verbatim term will be matched with the appropriate Preferred Term. The above analysis by dose will also be performed.

These analyses will present all unsolicited AEs, including SAEs and pIMDs (unless otherwise specified).

- The number and percentage of participants with at least one report of SAE classified by the MedDRA Primary SOC, HLT and PTs and reported after vaccine administration (Day 1) up to study end (6 months after last vaccination) will be tabulated with exact 95% CI.
- The number and percentage of participants with at least one report of causally related SAE classified by the MedDRA Primary SOC, HLT and PTs and reported after

vaccine administration (Day 1) up to study end (6 months after last vaccination) will be tabulated with exact 95% CI.

- The same tabulation will be presented for fatal SAEs.
- All SAEs will also be described in detail in a tabular listing.
- All pIMDs will also be described in detail in a tabular listing.
- All AEs/SAEs leading to study/intervention discontinuation from dose 1 up to study end will be tabulated.
- The percentage of participants with at least one report of pIMD classified by the MedDRA SOC, HLT and Preferred Terms and reported after vaccine administration (Day 1) up to study end (6 months after last vaccination) will be tabulated with exact 95% CI. The percentage of participants with at least one report of related pIMD classified by the MedDRA SOC, HLT and Preferred Terms and reported after vaccine administration (Day 1) up to study end (6 months after last vaccination) will be tabulated with exact 95% CI.
- For analysis of SAEs/pIMDs from first vaccination up to 6 months **post-last vaccination**, the reporting period will start at vaccination and will end at Day 183 **post-last vaccination** (i.e., day of last vaccination+183), computed as 6×30.5 days=183 days.
- The number and percentage of participants using concomitant medication (any medication and any antipyretic) during the 7-day and the 30-day follow-up period after each dose and overall will be tabulated with exact 95% CI.
- The number and percentage of participants using concomitant vaccination during the 30-day follow-up period after each dose and overall will be tabulated with exact 95% CI.
- Compliance in completing solicited events information will be tabulated after each dose and overall.

Some of the key safety analysis will be generated by age group at first vaccination (65-69 YOA, 70-79 YOA, ≥ 70 YOA and ≥ 80 YOA years) as mentioned below.

- The number and percentage of participants reporting each individual solicited administration site AE (any grade, Grade 3 and resulting in medically attended visit) and solicited systemic AE (any grade, Grade 3 and resulting in medically attended visit) during the 7-day follow-up period (i.e., the day of vaccination and 6 subsequent days) will be tabulated for each group after each dose and overall.

[figure not shown]
The number and percentage of participants with any unsolicited AEs during the 30-day follow-up period (i.e., the day of vaccination and 29 subsequent days) with its exact 95% CI will be tabulated by group and by MedDRA Primary SOC, HLT and PTs

- For clinicaltrials.gov and EudraCT posting purposes, percentage of participants of combined solicited and unsolicited non-serious adverse events during the 30-day follow-up period (i.e., the day of vaccination and 29 subsequent days) will be

produced by System Organ Class and preferred terms and according to occurrence of each event.

